12.1 Adverse Event (AE) (including Adverse Drug Reactions)

The medications for this study are government approved DAA regimens. Adverse Events and adverse drug reactions will be reported to the Therapeutic Goods Administration as per standard practice for PBS prescribed medications.

12.2 Serious Adverse Event (SAE) (including Serious Adverse Drug Reaction)

The medications for this study are government approved DAA regimens. Serious Adverse Events and serious adverse drug reactions will be reported to the Therapeutic Goods Administration as per standard practice for PBS prescribed medications.

13 Packaging, labeling, storage and accountability of clinical trial supplies

The medications for this study are government approved DAA regimens. The packaging, labelling and accountability of prescribed treatment will be as per the approved product information. Study medication will be supplied by the Pharmaceutical Benefits Scheme (PBS).

14 Biological samples

Dried Blood Spot samples (DBS) will be collected at Screening for all participants. These will be dried and stored and later tested for hepatitis C. The samples will also be used to look at potential transmission patterns (known as phylogenetics). Leftover samples from consenting participants will be stored and may be used for future unspecified hepatitis C related research until all of the samples have been used up or are no longer viable. Any future research using these samples will be approved by a Human research Ethics Committee prior to starting.

For participants on treatment which are re-viraemic at SVR12 or subsequent follow-up visits, a DBS sample and 10 mL of EDTA plasma will be collected for viral sequencing and resistance testing respectively. They will be used to compare with the Screening samples to determine if the virus is homogenous or heterogenous.

15 Statistics

A total of 60 Participants are planned for enrolment and evaluation as the overall ITT population. Cohorts A and B (30 patients each) will be evaluated sequentially and subsequently together using both ITT and per protocol based analyses.

15.1 Primary endpoint

Proportion of patients achieving confirmed SVR12 (defined as HCV RNA below the lower limit of quantitation at 12 weeks post treatment) in the intention-to-treat population (defined as all enrolled participants who received at least one dose of study drug). The ITT population consisting of patients commencing inpatient DAA treatment within public hospital services

15.2 Secondary Endpoints

- Proportion of patients with HCV RNA below the level of detection at 12 weeks post-treatment (SVR12) within each cohort by both ITT and PP analyses
- Proportion of patients with HCV below LLOQ at week 4 of therapy and ETR
- Proportion of patients completing DAA treatment course
- Proportion of patients with full (100%) and partial adherence (<50%, 50-80%, 81-99%) during treatment as assessed by in hospital medication charts and outpatient weekly self-report
- Uptake of DAA therapy during admission in patients suitable for study
- Safety: Rates and predictors of adverse events secondary to drug:drug interactions
- Sensitivity and specificity of finger prick POC testing compared to plasma HCV RNA at screening
- Proportion of patients completing recommended inpatient stay
- Changes in HRQOL
- Rates of re-attendance at subsequent planned study visits
- Rates and predictors of reinfection during follow-up

In those with a history of injecting drug use:

- Proportion of patients undergoing D&A evaluation during admission
- Proportion of patients initiating OST during admission
- Frequency and patterns of injecting behaviour following therapy for HCV

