Procedure	Screening	Baseline	On-treatment phase			SVR12	Follow-up 1 (SVR24)	Follow-up 2 (SVR36)	Follow-up 3 (SVR48)
			Hospital discharge ¹	Week 4	End of Treatment				
Study Week	-6 to 0	0	Variable	4	8	20	32	44	56
Visit Window (Days)									
Informed consent	X								
Medical history	X		X						
Physical measurements (height and weight)	X								
Liver function tests	X	X			X	X	X	X	X
Full blood count and biochemistry	X								
HCV RNA testing (local laboratory)	X			X	X	X	X ⁸	X ⁸	X ⁸
HCV RNA testing (finger-stick capillary whole-blood) ²	X					X	X	X	X
HCV genotyping (local laboratory) ³	X					X ⁸	X ⁸	X ⁸	X ⁸
HIV serology	X								
HBsAg	X								
Clinical assessment (including hepatic decompensation assessment)	X								
Fibrosis assessment (FibroScan or APRI) ⁴	X								
Pregnancy test (females - serum or urine) ⁵	X	X		X	X				
Treatment initiation		X							
Behavioural survey	X					X			X
EQ-5D-5L	X					X			X
Concomitant medication assessment ⁶	X	X	X	X	X	X			
Study drug adherence ⁷				X					
D&A evaluation		X		X					
Research Specimen Collection									
DBS Sample for Sequencing	X					X ⁸	X ⁸	X ⁸	X ⁸
EDTA Plasma for resistance testing (10mL)						X ⁸	X ⁸	X ⁸	X ⁸

1 Week 4 and End of Treatment visits will be conducted during hospitalisation where possible. If the participant is discharged, whilst on-treatment, Week 4 and End of Treatment will occur at outpatient viral hepatitis services.

2 HCV RNA finger-stick capillary whole-blood will be tested using the Xpert® HCV Viral Load assay on the Gene Xpert® II machine. During follow-up visits (SVR12, SVR24, SVR36 and SVR48), finger-stick capillary whole-blood will be used for HCV RNA and local laboratory HCV RNA may be performed if a positive HCV RNA is detected through the Xpert® HCV Viral Load assay.

3 HCV genotyping will only be performed during follow-up for participants identified with recurrent viraemia

4 Liver fibrosis will be assessed with a FibroScan if possible. Otherwise, an APRI score will be used for fibrosis assessment.

5 Pregnancy testing is not required for females of non-childbearing potential.

6 Concomitant medications will be assessed at Screening and updated at visits as appropriate. During follow-up concomitant medications will only be collected for those related to interactions with treatment of HCV.

7 Study drug adherence will be collected via telephone on a weekly basis for participants who are discharged prior to treatment completion.

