7.2 Secondary Objectives

- To evaluate the proportion of patients achieving confirmed SVR12 (undetectable HCV RNA at time point 12 weeks plus post treatment commencement) in patients hospitalised for IRID and commencing inpatient DAA treatment within public hospital services
 - To evaluate and compare the proportion of patients with undetectable HCV RNA at 12 weeks post-treatment (SVR12) within each cohort
 - To evaluate proportion of patients with HCV below LLOQ at week 4 of therapy and ETR
 - To evaluate DAA treatment completion rates
 - To evaluate adherence during treatment via in hospital medication charts and outpatient weekly self-report
 - To evaluate acceptability and feasibility of DAA commencement whilst an inpatient
 - To evaluate adverse events secondary to drug:drug interactions
 - To evaluate performance of finger prick POC testing compared to plasma HCV RNA at screening
 - To evaluate completion of duration of recommended inpatient stay and therapy for co-morbidities
 - To determine effect of HCV treatment on quality of life
 - To evaluate rate of re-call and re-infection at 6, 9- and 12-months post study enrolment
- In those who inject drugs:
- To evaluate engagement with D&A services and rates of OST initiation
 - To determine rates and patterns of injecting behaviour following therapy for HCV

8 Participant population

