10.3 Prior and concomitant medications

The prescribing information for all concomitant drugs should be consulted and reviewed carefully. The determinations listed in the respective contraindicated, warning, and precaution sections must be respected in order to prevent any potentially serious and/or life-threatening drug interactions.

Drug-drug interactions for each participant should be assessed on <http://www.hep-druginteractions.org/>. In case of any questions on potential interactions with a drug, please contact the study principal investigator.

Use of medications listed below within 2 weeks or 10 half-lives, whichever is longer, prior to study drug administration is contra-indicated (see Tables 1 and 2):

Table 2 Contraindicated concomitant medications with glecaprevir/pibrentasvir

Drug Class	Drug(s) within Class that are Contraindicated	Clinical Comments
Anticoagulants	Dabigatran	May increase dabigatran concentration potentially increasing risk of bleeding
Anticonvulsants	Carbamazepine	May decrease DAA exposure leading to a potential loss of therapeutic activity.
Antimycobacterial	Rifampin	May decrease DAA exposure leading to a potential loss of therapeutic activity.
Ethinyl estradiol-containing products	Ethinyl estradiol-containing medications (such as combined oral contraceptives and hormone replacement therapy)	Potential for ALT elevation
Gastrointestinal pro-kinetic agent	Cisapride	
Herbal Product	St. John's Wort (Hypericum perforatum)	May decrease DAA exposure leading to a potential loss of therapeutic activity.
HIV non-nucleoside reverse transcriptase inhibitor	Efavirenz Etravirine Nevirapine	May decrease DAA exposure leading to a potential loss of therapeutic activity.
HIV protease inhibitor	Atazanavir Darunavir	Potential for ALT elevation
HMG-CoA Reductase Inhibitors *	Atorvastatin Lovastatin Simvastatin	Potential for myopathy including rhabdomyolysis.

Immunosuppressant	Cyclosporin	Co-administration not recommended with cyclosporin dose >100mg per day
-------------------	-------------	--

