* Some HMG-CoA reductase inhibitors (including atorvastatin, lovastatin, or simvastatin) should not be taken with glecaprevir/pibrentasvir. Participants receiving these statins should either switch to pravastatin or rosuvastatin prior to the first dose of study drug or interrupt statin therapy throughout the treatment period and until 30 days after the last dose. If switching to or continuing pravastatin or rosuvastatin, it is recommended to reduce the pravastatin dose by 50% or limit the rosuvastatin dose to 10 mg daily while on treatment.

Table 3 Contraindicated concomitant medications with sofosbuvir

Drug Class	Drug(s) within Class that are contraindicated	Clinical Comments
Analeptics	Modafinil	Coadministration of sofosbuvir with modafinil is expected to decrease the concentration of sofosbuvir, leading to reduced therapeutic effect of sofosbuvir. Such coadministration is not recommended.
Antiarrhythmics	Amiodarone	Coadministration of amiodarone with another direct acting antiviral may result in symptomatic bradycardia. If coadministration is required, cardiac monitoring is recommended.
Anticoagulants	Vitamin K agonists	Close monitoring of the INR is recommended, as liver function may change with sofosbuvir treatment.
Anticonvulsants	Carbamazepine Phenytoin Phenobarbital Oxcarbazepine	May decrease DAA exposure leading to a potential loss of therapeutic activity, therefore not recommended.
Antimycobacterials	Rifabutin Rifampin Rifapetine	May decrease DAA exposure leading to a potential loss of therapeutic activity, therefore not recommended.
Herbal Supplements	St John's wort	May decrease DAA exposure leading to a potential loss of therapeutic activity, therefore not recommended.
HIV Protease Inhibitors	Tipranavir Ritonavir	May decrease DAA exposure leading to a potential loss of therapeutic activity, therefore not recommended.

11 Study procedures

Screening Visit (Week -6 to Week 0) – All participants

- Informed consent: At the screening visit, participants will provide written and informed consent prior to any study-specific procedures.
- Medical history: A medical history will be taken
- Physical measurements: Height and body weight.
- Clinical laboratory tests: At a minimum, liver function tests, biochemistry and full blood count tests will be collected at Screening (or used from admission bloods).
- HCV RNA (local laboratory): Quantitative HCV RNA

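### Adverse events from drug interactions are a secondary endpoint, but no visit or weekly call includes an adverse-event enquiry, so non-serious symptoms after discharge are not systematically sought

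*Protocol*

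**What the plan says.** The objective in section 7.2 is "To evaluate adverse events secondary to drug:drug interactions", and the matching endpoint in section 15.2 is "Safety: Rates and predictors of adverse events secondary to drug:drug interactions". The synopsis carries both.

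Section 10.3 shows which harms are expected. For three statins Table 2 gives "Potential for myopathy including rhabdomyolysis". Those statins must be switched or stopped, but pravastatin and rosuvastatin may be taken during treatment: "it is recommended to reduce the pravastatin dose by 50% or limit the rosuvastatin dose to 10 mg daily while on treatment". In Table 3, which concerns sofosbuvir and so Cohort B only, the amiodarone entry warns of symptomatic bradycardia and adds "If coadministration is required, cardiac monitoring is recommended". The entry for vitamin K anticoagulants reads "Close monitoring of the INR is recommended, as liver function may change with sofosbuvir treatment".

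On contact after discharge, footnote 7 of both Schedules of Assessments says "Study drug adherence will be collected via telephone on a weekly basis for participants who are discharged prior to treatment completion". Sections 9.2 and 10.2 describe the same weekly contact, also for adherence alone.

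Sections 12.1 and 12.2 say that adverse events and serious adverse events go to the Therapeutic Goods Administration under standard practice for subsidised medicines. Section 16 gives oversight of serious events to the medical monitor.

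**The concern.** A rate can be interpreted only if every participant is asked the same question at comparable times. Here the exposure side of the endpoint is scheduled, because concomitant medicines and possible interactions are reviewed through treatment and again at SVR12. The outcome side is not: nothing in the visit plan asks whether the participant has had a symptom.

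The gap matters most after discharge. Observed dosing stops, the remaining tablets are handed over at the discharge visit (section 10.2), and the regular contact left is a call about adherence. If few interaction events were then reported, nobody could say whether the regimens were well tolerated alongside other medicines or whether the events were never elicited. Outpatient treatment is also longer in the 8-week cohort, so the shortfall need not be equal in the two cohorts.

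This is not a matter to leave to the statistical analysis plan, which cannot recover events that nobody asked about.

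**Working it through.** The protocol gives no figure for this endpoint, so there is none to reproduce. The check is a reading of every place where collection could be specified, followed by a short calculation of outpatient exposure.

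**Where collection could be specified**

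| Place | What it provides | Adverse-event enquiry? |
|---|---|---|
| Schedule, Cohort A | 21 rows | 0 of 21 |
| Schedule, Cohort B | 21 rows | 0 of 21 |
| On-treatment visits after Baseline | A: discharge, Week 4, End of Treatment; B: discharge, End of Treatment | 0 of 3 (A), 0 of 2 (B) |
| Section 11 visit lists | Laboratory tests, pregnancy test, medication/interaction check, adherence, questionnaires | None; there is no list for the discharge visit |
| Weekly contact (9.2, 10.2, footnote 7) | Adherence | None |
| Section 12 | Reporting to the regulator | No step that seeks events |
| Section 16 | Oversight of serious events | Acts on events already known |

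**What the scheduled items do cover**

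- Liver tests can show ALT elevation. After Baseline the only on-treatment test is at End of Treatment.
- HCV RNA can show lost antiviral activity.
- The medication/interaction check records which medicines are taken. Section 10.3 describes it as a look-up on an interaction website.
- Clinical assessment is at Screening only. Medical history is at Screening and hospital discharge.

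What remains uncovered is non-serious symptomatic harm after discharge. Examples are myopathy on dose-limited pravastatin or rosuvastatin (either cohort), and bradycardia with amiodarone or bleeding on a vitamin K anticoagulant (Cohort B). The last is an inference from the INR advice; the table entry does not itself name bleeding.

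**How much treatment falls after discharge (illustration)**

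Inputs: treatment length T = 56 days (A) or 28 days (B), from section 10.1. Stay L = 12 days, the average in the single-centre audit cited in section 5. Days from admission to first dose k = 3, an assumption, since section 5 says only that treatment should start within the first few days.

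Share after discharge = max(0, T − (L − k)) / T

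- Cohort A: (56 − 9)/56 = 47/56 = 84%
- Cohort B: (28 − 9)/28 = 19/28 = 68%

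Varying k with L = 12:

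- k = 0: 44/56 = 79% (A), 16/28 = 57% (B)
- k = 5: 49/56 = 88% (A), 21/28 = 75% (B)

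Varying L with k = 3:

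- L = 7, the edge of the eligibility rule: 52/56 = 93% (A), 24/28 = 86% (B)
- L = 42, the upper end of the antibiotic durations in section 5: 17/56 = 30% (A), 0/28 = 0% (B)

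Whenever discharge comes before treatment day 28, a Cohort A participant who takes the full course has 56 − 28 = 28 more outpatient treatment days than a Cohort B participant with the same stay. In the 12-day case, 47/7 and 19/7 leave room for 6 and 2 complete weekly calls. These are maxima, because not every call will succeed.

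**The case against.** The strongest reply is that events can come to light without a schedule row. Both schedules repeat the medical history at hospital discharge. Before discharge, dosing is observed daily and charted (section 10.2), and section 17.1 counts medical records, progress notes and ECG tracings as source documents. Staff review medicines and interactions with participants at set visits. Serious events reach the medical monitor. The eCRF is not shown and might hold an adverse-event page, and section 9.4 shows that forms outside the schedule exist.

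This stands in part. A reader might infer that symptomatic harms would be counted only if the participant volunteers them, or that they cannot be recorded at all. The protocol does not support either reading: ward staff may see and chart events, and the discharge history is a clinical enquiry during treatment. But none of these routes is specified as collection for the endpoint, and ward charting and the discharge history end at discharge.

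A second reply concerns exposure. Dabigatran and the three listed statins are contraindicated, prohibited medicines bar treatment, and the amiodarone and vitamin K entries apply only where sofosbuvir is given. This also stands. A reader might therefore see a defect in the schedules' silence on INR and cardiac monitoring. It is not one: both are clinical care for the few participants on those medicines, and irrelevant to Cohort A. The exposures the protocol allows for are fewer than the tables suggest, but they are not absent.

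Finally, this is one of many secondary endpoints in a 60-participant study with no formal sample size, and predictors would be weakly estimable in any case. That limits the stakes to the rate, but an uninterpretable rate is still a failed endpoint, and it is cheap to prevent.

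**Conclusion.** The point holds in a limited form. The protocol names interaction-related adverse events as an objective and an endpoint but specifies no enquiry about adverse events at any visit or weekly call in either cohort. Followed exactly, it leaves non-serious symptomatic events after discharge without systematic ascertainment. The expected effect is a rate biased downward, possibly by different amounts in the two cohorts.

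The size of that bias cannot be computed, because the documents give neither an expected event rate nor a probability of spontaneous report. What can be sized is the exposure: about 84% of treatment days in Cohort A and 68% in Cohort B after discharge, given a 12-day stay and first dose at day 3. These are illustrations and not bounds. The audit average comes from one centre, eligibility requires only an anticipated stay of more than a week, and the 2-6 weeks in section 5 describes antibiotic courses for many of these infections rather than the range of stays in this trial.

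The conclusion concerns the interaction-event rate only. SVR12 does not depend on it. The change should be made, but it does not threaten the trial's main result.

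**What to change.** 1. Add an adverse-event item to both Schedules of Assessments and to section 11 at hospital discharge, Week 4 (Cohort A) and End of Treatment. Section 11 needs a short discharge-visit list for this.
2. Add one adverse-event question to the existing weekly adherence call.
3. Record onset, seriousness, relation to study drug and suspected interacting medicine in the eCRF. Limit non-serious events to those suspected to be due to study drug or an interaction, or that stop study drug, so that events of the admitting illness do not swamp the data.

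If participants have been treated before the change, report their adverse-event data separately, since post-discharge events can be recovered only in part.

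The cost is a short amendment, one eCRF form and a little extra site time per contact. No new visit or call is needed.

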15.3 Analyses

Proportions and 95% confidence intervals will be reported for both the primary and secondary virological endpoints. These will be assessed for both the PP and the ITT populations. Results will be stratified by HCV genotype/subtype.

Sub-group analysis of treatment efficacy (SVR12) in the ITT population will be evaluated for the following variables: demographic factors (age, gender); virological factors (pre-treatment HCV RNA, genotype); HIV co-infection. Additional treatment efficacy evaluations will be conducted among the per protocol study population, defined as Participants who receive >80% of planned treatment.

The impact of adherence (<50%, 50-80%, 81-99%), 100/100 adherence, on-treatment adherence and early discontinuation on SVR will also be evaluated.

A final full statistical analysis plan will be written and signed off by the Protocol Steering Committee prior to final study data lock.

16 Data Safety and Monitoring Board (DSMB)

This project is conducted as a Phase IV trial using PBS approved medication and as such, a DSMB will not be used. The medical monitor, [name] will oversee all serious adverse events for TOPIC. As [name] is also Co-Investigator and clinician at Prince of Wales Hospital, which is one of the recruiting sites, should an SAE occur in a patient under [name] care, the

project team will seek an independent review of the SAE from a suitably qualified independent Infectious Diseases Specialist or Hepatologist.

17 Data collection, source documents and record retention

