9.1 Summary of study design

[figure not shown]
The study will be conducted as a Phase IV open-label single-arm multicenter study consisting of two sequential cohorts: Cohort A (8 weeks of glecaprevir/pibrentasvir) and Cohort B (4 weeks of sofosbuvir/glecaprevir/pibrentasvir).

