10.2 Dosing and Administration

Participants should be instructed to take study medication with food at approximately the same time each day. Dose modifications are prohibited. The first study drug dosing will commence in hospital at Baseline (day 0). The start date and the last dose of the regimen should be documented in the subject's source documents and appropriate eCRF.

Participants should be instructed to swallow the study drug tablets whole. Participants should be instructed to only remove the tablets from the packaging immediately prior to dosing.

For a missed dose of study drug, participants should be instructed to take the missed dose of study drug as soon as possible during the same day. However, no more than the daily dose of sofosbuvir and glecaprevir/pibrentasvir should be taken on any calendar day. Participants should be cautioned never to double the next dose with a missed dose of study drug under any circumstances.

Dispensing

Participants will be dispensed with their study medication daily prior to hospital discharge. At the hospital discharge visit, participants will be dispensed with the remaining study medication for the treatment regimen. Participants should receive counseling on the importance of adherence in regard to virologic response and potential development of resistance.

Adherence

Adherence monitoring will be daily observed, and the date and time will be recorded in the medical records prior to hospital discharge. Following hospital discharge, participants will be contacted weekly for self-reported treatment adherence.

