- HCV Genotype (local laboratory): HCV genotype should be collected at screening. Historical participant genotype results are acceptable if these were conducted within 5 years from Screening.
- HCV RNA (point-of-care): A finger-stick capillary whole-blood sample will be collected for the GeneXpert. This may be repeated if an invalid result is obtained in the absence of a local laboratory HCV RNA.

- HIV and HBV serology: Anti-HIV Ab and HBsAg results within 5 years prior to Screening are also acceptable.
- Fibrosis Assessment: Liver fibrosis will be measured using a FibroScan where possible. An AST to Platelet Ratio Index (APRI) will be considered as an acceptable alternative if a FibroScan is not possible.
- Pregnancy test: All females of child-bearing potential will have a serum or urine pregnancy test. This will not be required for females of non-childbearing potential. Determination of postmenopausal status will be recorded during the Screening period based on participant history.
- Behavioural survey and EQ-5D-5L.
- Clinical assessment and concomitant medication assessment / DDI assessment.
- Dried Blood Spot sample.

The following study visits are for participants who commence treatment only.

Baseline visit (Week 0)

Eligible participants who meet the treatment inclusion criteria and meet none of the exclusion criteria will proceed to the baseline visit. This visit must be completed prior to hospital discharge.

The following procedures will be conducted:

- Concomitant medications / DDI assessment: These will be updated from the Screening visit as necessary.
- Pregnancy test: Urine or serum pregnancy tests.
- Full blood count and biochemistry
- Treatment initiation: Participants will be administered the study drug at the site with dosing instructions at the baseline visit.

Week 4 (Cohort A only)

Participants in Cohort A will have an on-treatment visit at Week 4. The following procedures will be conducted:

- HCV RNA testing (local laboratory)
- Pregnancy test (women of child-bearing potential; serum or urine)
- Concomitant medication assessment / DDI assessment
- Adherence

End of Treatment – (Week 8 – Cohort A, Week 4 – Cohort B)

The date of the last dose of study medication will be collected. The end of treatment visit will be either Week 8 or Week 4, depending on the cohort. The following procedures will be conducted:

- HCV RNA testing (local laboratory)
- Liver function tests

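### Section 15.3 puts the week-4 virological response in a per-protocol set that, in Cohort A, depends on doses due after week 4 and sets a different pre-test adherence standard from Cohort B

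*Protocol*

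**What the plan says.** Protocol section 15.2 lists as a secondary endpoint: "Proportion of patients with HCV below LLOQ at week 4 of therapy and ETR". Section 15.3 then states: "Proportions and 95% confidence intervals will be reported for both the primary and secondary virological endpoints", followed by "These will be assessed for both the PP and the ITT populations". No virological endpoint is excepted.

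The PP set is defined once, in section 15.3: "per protocol study population, defined as Participants who receive >80% of planned treatment". It is not tied to an endpoint or to the time of an assessment. The ITT set is "defined as all enrolled participants who received at least one dose of study drug" (section 15.1).

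Planned treatment is 8 weeks in Cohort A and 4 weeks in Cohort B (section 9.1; section 10.1, Table 1). Section 11 adds: "The end of treatment visit will be either Week 8 or Week 4, depending on the cohort". Week 4 is thus the middle of the course in Cohort A and its end in Cohort B.

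**The concern.** Membership of a set used to analyse a week-4 measurement should be settled by what has happened up to week 4. With a threshold on the whole course this is true in Cohort B. In Cohort A it is not, because half the course is still to come when the sample is taken.

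Two faults follow for Cohort A. A participant who took every dose to week 4 and then stopped loses a valid week-4 result from the PP denominator. A participant who took few doses early but nearly all later doses is counted as per protocol at week 4, although adherence up to the test was poor.

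The protocol itself expects stopping in weeks 5-8. Section 5 foresees that a significant proportion may not complete 8 weeks, and hypothesis 2 in section 6 predicts better completion in Cohort B. At stake are the meaning of Cohort A's week-4 PP figure and whether it can be read beside Cohort B's.

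**Working it through.** The protocol gives no figure of its own on this point, so there is none to reproduce. The first two steps need no assumption about behaviour; the last two do.

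**Inputs from the protocol**
- Planned daily doses: 8 × 7 = 56 in Cohort A and 4 × 7 = 28 in Cohort B (sections 9.1 and 10.1).
- PP threshold: more than 80% of planned treatment (section 15.3).
- Dosing ceiling: "no more than the daily dose of sofosbuvir and glecaprevir/pibrentasvir should be taken on any calendar day" (section 10.2), so at most 28 doses by week 4.
- Cohort size: 30 each (section 8.1).

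**Step 1: doses needed after the week-4 test**

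Minimum doses for PP = floor(0.80 × planned) + 1.

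| | Cohort A | Cohort B |
|---|---|---|
| 80% of planned doses | 0.80 × 56 = 44.8 | 0.80 × 28 = 22.4 |
| Minimum for PP | 45 | 23 |
| Most possible by week 4 | 28 | 28 |
| Needed after week 4, at the least | 45 − 28 = 17 | 0 |

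Counting days instead of doses gives the same result, because week 4 is 50% of Cohort A's course either way.

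**Step 2: adherence needed before the test**

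In Cohort A, a participant who takes all 28 doses of weeks 5-8 needs only 45 − 28 = 17 of the first 28, and 17/28 = 61%. In Cohort B the requirement is 23/28 = 82%.

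**Step 3: size of the upward effect (illustration)**

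The protocol does not give a completion rate or a week-4 response by later stopping. Assume a constant stopping rate, 75% completion of 56 days, and week-4 response of 95% in those who reach day 45 and 70% in those who stop between days 28 and 45.

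- Daily rate h = −ln(0.75)/56 = 0.00514.
- Reach day 28: exp(−28h) = 0.866.
- Reach day 45: exp(−45h) = 0.794.
- Dropped for stopping after day 28: 0.866 − 0.794 = 0.072, and 0.072 × 30 = 2.2, about 2 participants.
- Response among all who reach day 28: (0.794 × 0.95 + 0.072 × 0.70)/0.866 = 0.929.
- PP figure 0.950, a shift of 2.1 points upward.

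The same formula over a range of assumed completion rates:

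| Completion | Reach day 28 | Reach day 45 | Dropped | Shift |
|---|---|---|---|---|
| 60% | 0.775 | 0.663 | 11.1% | 3.6 points |
| 75% | 0.866 | 0.794 | 7.2% | 2.1 points |
| 90% | 0.949 | 0.919 | 3.0% | 0.8 points |

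The shift is zero if later stoppers respond as well at week 4 as those who continue.

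**Step 4: the opposite effect**

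Under 75% completion the PP set has about 0.794 × 30 = 24 members. If 2 of the 24 had entered with only 17-22 of their first 28 doses, and their week-4 response were 70% against 95% (assumed), the figure would fall by (2/24) × 25 = 2.1 points. That is enough to cancel step 3.

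**The case against.** **The PP week-4 figure supports no planned conclusion.** The endpoint is secondary. The only objective that speaks of comparing concerns SVR12 (section 7.2), and hypothesis 2 concerns completion and SVR12. A reader might infer that a cohort comparison at week 4 is biased, but the protocol plans none. Week 4 is also end of treatment in Cohort B, so the two figures differ in meaning in any case. This stands and limits the weight of the point.

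**An unaffected result is already required.** ITT includes everyone who received a dose and is reported for the same endpoint. This also stands.

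**The bias could go either way.** A reader might infer that Cohort A's figure is inflated and Cohort B's is not. The documents do not support that: the rule that drops later stoppers also admits early poor adherers, and the protocol has no data on either group. Nor would the same participant always stay in under Cohort B, since 22 or fewer of 28 doses means exclusion there too. The contrast holds only for someone with at least 23 doses by week 4.

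**The size is assumed and small.** Counting everyone who stops between days 23 and 45 gives 0.889 − 0.794 = 9.5%, about 3 of 30, and a 2.7-point shift. That count includes people who stop on days 23-28, before the test, so it overstates selection on later behaviour. The 2.1 points from day 28 onward are less than one participant (1 of 26 is 3.8 points). Sampling error is far larger: the exact 95% interval for 25 of 27 is 76% to 99%.

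**It could be left to the SAP.** Section 15.3 announces a full SAP before data lock, and section 15.2 names both analysis sets only in the SVR12 item. This does not dispose of the point. Section 15.3 itself fixes both the PP rule and its use for every virological endpoint, so this is a stated rule that works badly, not a detail left open.

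**Conclusion.** The point holds and is minor. As written, Cohort A's week-4 PP result is conditioned on at least 17 doses due after the test, and its pre-test adherence can be as low as 61% where Cohort B requires 82%. Both statements follow from the protocol's own figures alone.

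The result is potentially biased and is not on the same basis as Cohort B's. The bias is upward if later stoppers respond less well at week 4, and downward if early poor adherers are admitted. The protocol does not allow the net direction to be determined. The illustrative upward shift of about 2 points (0.8 to 3.6 for 90% to 60% completion) rests wholly on the assumed constant stopping rate, completion and 70% against 95% response. The ITT week-4 result and the SVR12 analyses are untouched.

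**What to change.** Add one sentence to section 15.3 and carry it into the SAP: for the week-4 endpoint only, the per-protocol set in both cohorts is participants who received more than 80% of the doses planned for days 1-28 (at least 23 of 28). Keep more than 80% of the full course for ETR and SVR12.

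The doses required after week 4 in Cohort A fall from 17 to 0, and both cohorts then meet the same pre-test standard. Cohort B's set does not change. No new data are needed, since section 10.2 already has adherence observed daily in hospital and self-reported weekly after discharge. The only cost is a second PP definition to report and label.

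Reporting week 4 in ITT only would also remove the problem, but would give up the PP result.
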